6.4.2 Secondary Efficacy Variables

Secondary efficacy variables will be collected at Visit 2, Visit 4 and Visit 4c. The secondary efficacy variables are:

- CFVR (ratio)
- LAD resting mean diastolic flow velocity (m/s)
- LAD hyperaemic flow velocity (m/s)
- Measurements of left ventricular (LV) systolic and diastolic function, more specifically:
 - LV Ejection Fraction (LVEF) at rest (%)
 - LV Global Longitudinal Strain (GLS) at rest and at hyperaemia (%)
 - LV Global Circumferential Strain (GCS) at rest (%)
 - LV longitudinal early diastolic strain rate (s⁻¹)

Change at visit 4c (12 weeks) and at visit 4 (4 weeks) from Baseline in CFVR are the second and the third secondary efficacy endpoints respectively.

Change at visit 4 (4 weeks) and at visit 4c (12 weeks) on all other secondary variables will be tested as other secondary endpoints and exploratory endpoints respectively.

Baselines are defined as described in section 6.3.

For the CFVR only valid measurements will be used for the analysis. Valid measurement at each visit will be defined by the CFVR Core lab by means of a validity flag in the raw dataset (EVALPAT = Valid).

For all the other variables if images are not presented/not measurable, they are considered NOT VALID. If measurable, they are graded as POOR/ACCEPTABLE/GOOD depending on quality. All data except NOT VALID should be analysed.

6.4.3 Additional Efficacy Variables

Not Applicable.

6.5 Drug Concentration Measurements and Pharmacokinetic Parameters

Venous blood samples for the determination of plasma concentrations of AZD5718 will be collected at the time points presented in the study assessments schedule. Standard model population PK parameters will be reported in a separate report.

Plasma concentrations below the limit of quantification (LoQ) after first dose of IP will be set to LoQ/2.

6.5.1 Handling of Pharmacokinetic Parameter Outliers

Not applicable.

Distribution:

Original:

Copy:

TPCA025 Version 2 (based on TPQA036 Version 2)

Sponsor:	AstraZeneca AB	Protocol/CIP Number:	D7550C00003
CIL Project Number:	40343		

6.6 Safety Assessments

Safety assessments include AEs, clinical laboratory safety evaluations (haematology, serum biochemistry and urinalysis), vital signs (blood pressure, pulse rate and pulse oximetry), physical examination and 12-lead ECG.

6.6.1 Extent of Exposure and Compliance to Study Treatment

As per protocol, subjects start the study IP at the day of randomization (Visit 2). Then, randomized patients will be dispensed with one bottle of IP at each dispensing visit. Dispensation will take place at the following study visits:

- Visit 2 (Randomization),
- Visit 4 (4 weeks),
- Visit 4b (8 weeks).

Dose at Visit 2 (day 1), Visit 3 (day 14), Visit 4 (4 weeks) and Visit 4c (week 12) will be given by study personnel at the study site. The exact dose intake time before Visit 3, Visit 4 and Visit 4c will be recorded on a Diary Card. The Diary Cards will be given to the patients at the randomization visit and the patients will be asked to fill in the dose intake information (date and time) at home.

Exposure and compliance are calculated as follow:

Exposure

Exposure (days) will be calculated for subjects in the Safety Analysis Set as the total number of days on study drug (i.e., gaps in dosing due to study drug interruption will not be takenout from the calculation). Exposure will be calculated as the study drug dose last date minus study drug dose first date plus one. If any of the first or last dates are missing, then imputed dates will not be used, and study drug exposure will be set to missing.

Actual exposure (days) will be calculated as the total number of days of effective study drug intake (i.e., gaps in dosing due to study drug interruption will be taken-out from the calculation). In this way, the subject's dosing can be reduced to a series of unbroken intervals within each of which exposure will be calculated as study drug dose stop date minus the study drug dose start date plus one. Actual exposure will be calculated as the sum of exposures over all the unbroken intervals.

If any of the start or stop dates are missing for an interval, study drug exposure for that interval will be set to missing. Imputed dates on first and last dose will not be used. Actual exposure will be the sum over only the intervals where drug exposure was not set to missing.

Cumulative exposure over time (day) will also be computed based on exposure, using the following duration (days) categories:

• >= 7,

• >= 14,

Distribution:

Original:

Copy:

TPCA025 Version 2 (based on TPQA036 Version 2)

of

STATISTICAL ANALYSIS PLAN

Sponsor:	AstraZeneca AB	Protocol/CIP Number:	D7550C00003
CIL Project Number:	40343		

- >= 28,
- >= 56,
- >= 84.

Compliance

During the single-blind treatment period, subjects are supposed to take once daily if on high dose and once daily if on low dose of AZD5718 or matching placebo according to the dosing schedule. Overall compliance to the dosing schedule will be examined for subjects in the Safety Analysis Set.

The percent compliance is defined as the total number of tablets consumed divided by the total number of tablets that should have been taken:

- (Total number of tablets consumed) x 100 / [(Exposure) x 2] for subjects on of AZD5718 or matching placebo and
- (Total number of tablets consumed) x 100 / (Exposure) for subjects on AZD5718 or matching placebo

where, total number of tablets consumed will be calculated as: Total number of tablets dispensed – Total number of tablets returned. The quantity of study drug dispensed to and returned by the subject will be counted and recorded on the drug accountability eCRF page.

No replacement of missing data will be performed. Therefore, if one of the total number of tablets dispensed, total number of tablets returned, or duration of exposure is missing the resulting compliance will be missing.

Compliance will also be computed using the following categories:

- < 80%
- \geq 80% to < 120%
- ≥ 120%

6.6.2 Adverse Events

Adverse Events (AE) will be collected from time of the first dose throughout the treatment period and including the Off-treatment phase (see section 6.2.3 for the phase definition). SAEs will be recorded from the time of informed consent.

After the imputation of AE start date and AE end date as described in section 7.3, AEs will be assigned to the period where they start according to the following algorithm:

If both the start date and start time of an AE are known, then:

- If the AE starts prior to the first dose of IP, then the AE will be assigned to the Baseline phase
- If the AE starts on or after the first dose of IP through 7 days after the date of the last dose of IP (inclusive), then the AE will be assigned to the On-treatment phase,

TPCA025 Version 2 (based on TPQA036 Version 2) Original:

Effective Date: 27th August 2017 Prior Effective Date: 21st December 2016

Distribution:

Sponsor:	AstraZeneca AB	Protocol/CIP Number:	D7550C00003
CIL Project Number:	40343		

• If the AE starts after the date of last dose of IP + 7 days (not inclusive), then the AE will be assigned to the Off-treatment phase.

If only the start date of an AE is known, and the start time of the AE is unknown, then:

- If the AE starts prior to the date of the first dose of IP, then the AE will be assigned to the Baseline phase,
- If the AE starts on or after the date of the first dose of IP through 7 days after the date of last dose of IP (inclusive), then the AE will be assigned to the On-treatment phase,
- If the AE starts after the date of last dose of IP + 7 days (not inclusive), then the AE will be assigned to the Off-treatment phase.

If the start date of an AE is completely missing, the AE should be assigned as follow:

- If the end-date is known:
 - If the end-date is before the date of first study IP then the AE will be assigned to the Baseline phase
 - If the end-date is on or after the date of first IP, no assignation can be done.
- If the end-date is completely missing no assignation can be done

The way the SAEs will be assigned to a specific period will be different for the first IA and second IA/final analysis.

First IA considerations

After the AE allocation to corresponding study phase, also the AE seriousness part of the event will be allocated to the corresponding study phase by means of the date in which the AE becomes serious.

After the imputation of the AE becomes serious as described in section 7.3, the SAE will be assigned to the period where it starts according to the following algorithm:

- If the date in which the AE becomes serious is prior to the date of the first dose of IP, then the SAE will be assigned to the Baseline phase,
- If the date in which the AE becomes serious is on or after the date of the first dose of IP through 7 days after the date of last dose of IP (inclusive), then the SAE will be assigned to the On-treatment phase,
- If the date in which the AE becomes serious is after the date of last dose of IP + 7 days, then the SAE will be assigned to the Off-treatment phase.

If the date in which the AE became serious is completely missing, the SAE will be assigned according to the AE start date and time.

The SAE assignation is used only to identify cases in which the AE starts as Non-serious in the On-treatment phase and becomes Serious in the Off-treatment phase. In cases like these, the AE will be reported as one single AE in the listings, but it will be summarized as one non-serious AE in the On-treatment tables and one SAE in the Off-treatment tables.

TPCA025 Version 2 (based on TPQA036 Version 2) Original:

Copy:

Effective Date: 27th August 2017 Prior Effective Date: 21st December 2016

Distribution:

Sponsor:	AstraZeneca AB	Protocol/CIP Number:	D7550C00003
CIL Project Number:	40343		

Second IA and final analysis considerations

If the AE started in the on-treatment phase and became serious in the off-treatment phase, the AE will be considered as serious from the start, i.e. in the on-treatment phase as well. The AE will be reported as one single record in the listing.

A drug-related AE is defined as any AE with a reasonable possibility of causal relationship to study treatment as assessed by the investigator or with missing assessment of the causal relationship.

The coding dictionary for this study will be the Medical Dictionary for Regulatory Activities (MedDRA) version 20.0 or higher.

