6.3 Recording of adverse events

6.3.1 Time period for collection of adverse events

Adverse Events will be collected from time of the first dose throughout the treatment period and including the follow-up period.

SAEs will be recorded from the time of signing ICF.

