Missing onset dates (where UN, UNK and 0000 indicate unknown or missing Day and Month and Year respectively for partial missing dates; while completely missing dates would be left empty):

- Completely missing dates will be not imputed
- If the day is missing and the month and year are different from the month and year of the first dose of study drug, assume YYYY-MMM-01. If the month and year are the same as the first dose of study drug month and year and the end date (after any imputation) is on or after (including still on-going at the end of the study) the first dose of study drug, then assume the date of the first dose of study drug. If the month and year are the same as the first dose of study drug month and year and the end date (after any imputation) is prior to the first dose of study drug, then assume the end date of the first dose of study drug for the end date (after any imputation) is prior to the first dose of study drug, then assume the end date for the onset date.
- If the month is missing and the year is different from the year of first dose of study drug, assume YYYY-JAN-01 of the collected year. If the year is the same as the first dose of study drug year and the end date (after any imputation) is on or after (including still ongoing at the end of the study) the first dose of study drug, then assume the date of the first dose of study drug. If the year is the same as the first dose of study drug and the

TPCA025 Version 2 (based on TPQA036 Version 2) Original:

Copy:

Effective Date: 27th August 2017 Prior Effective Date: 21st December 2016

Sponsor:	AstraZeneca AB	Protocol/CIP Number:	D7550C00003
CIL Project Number:	40343		

end date (after any imputation) is prior to the first dose of study drug, then assume the end date for the onset date.

After applying these rules, if the imputed AE onset date is after a complete AE end date or date of death, the imputed onset date will be the same as the complete AE end date/ date of death.

With regard to the AE becomes serious date, if after applying all these rules the imputed AE becomes serious date is missing or before the AE start date, then the imputed AE becomes serious date will be the same as the AE start date.

Of note that missing start dates for concomitant medications will not be imputed.

Imputation of AE / Concomitant Medication Stop Date:

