8.8.2 Adverse Events

AEs will be assigned to the study phases as described in section 6.6.2.

Unless otherwise specified, AEs and SAEs will be summarized using the Safety Analysis Set by treatment group and by cohort of patients. Percentages will be based on the total numbers of subjects in the treatment group.

Subjects with multiple events in the same category will be counted only once in that category. Subjects with events in more than 1 category will be counted once in each of those categories. Unless otherwise specified On-treatment and Off-treatment phases will be reported separately for each summary table.

The following summary tables will be reported:

An overview table for all the AEs.

The number and percentage of subjects with the most common AEs (frequency>3%) for each Preferred Term (PT);

Distribution:

Original:

Copy:

TPCA025 Version 2 (based on TPQA036 Version 2) Effective Date: 27th August 2017 Prior Effective Date: 21st December 2016

Sponsor:	AstraZeneca AB	Protocol/CIP Number:	D7550C00003
CIL Project Number:	40343		

The number and percentage of subjects with any AEs for each System Organ Class (SOC) and PT;

The number and percentage of subjects with any AEs by maximum intensity for each PT;

The number and percentage of subjects with any AEs by investigator's causality assessment for each PT;

The number and percentage of subjects with AEs with outcome of death for each SOC and PT;

The number and percentage of subjects with AEs with outcome of death and with causality related to study drug for each SOC and PT in the On-treatment phase.

Key subject information for all subjects with AEs with outcome of death (On-treatment and Off-treatment phases together in the same table).

Time from first dose to AE (day) will be calculated as start date of the AE minus date of first dose +1. Time from last dose to death (day) will be calculated as death date minus date of last dose +1. Time from first dose to death (day) will be calculated as death date minus date of first dose +1. Durations will be calculated only for fully completed dates.

The number and percentage of subjects with death.

The number and percentage of subjects with any SAEs for each SOC and PT;

The number and percentage of subjects with any SAEs with causality related to study drug for each SOC and PT in the On-treatment phase.

Key subject information for all subjects with SAEs.

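### AEs with a completely missing start date that did not end before first dose get no study phase, so the on-/off-treatment n (%) tables have no place for them

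*SAP*

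**What the plan says.** SAP 6.6.2 assigns each AE to the baseline, on-treatment or off-treatment phase by its start date, after the imputation in SAP 7.3. When no part of the start date is known it has a separate rule, introduced by "If the start date of an AE is completely missing, the AE should be assigned as follow". The rule has three branches:

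- An event known to have ended earlier than first dose goes to baseline.
- For an event that ended later than that, the SAP states: "If the end-date is on or after the date of first IP, no assignation can be done"
- Where neither date was recorded, the outcome is the same: "If the end-date is completely missing no assignation can be done"

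SAP 7.3 does not rescue the last two branches, since for onset dates it says "Completely missing dates will be not imputed". A partial onset date is treated differently. If the known part matches first dose and the event ended on or after first dose or is ongoing, the rule is "then assume the date of the first dose of study drug", which puts the event on-treatment.

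For the tables, SAP 8.8.2 says "Unless otherwise specified On-treatment and Off-treatment phases will be reported separately for each summary table". The interim AE tables in SAP 8.10.3 are on-treatment only.

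On collection, Protocol 6.3.1 says "Adverse Events will be collected from time of the first dose throughout the treatment period" and on into follow-up, while SAEs are recorded from consent. Protocol 8.5.3 places all AEs in a baseline, on-treatment or off-treatment period according to when they start.

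**The concern.** An event without a phase has no n (%) table to enter. The rule can therefore only take events out of the reported on- and off-treatment counts; it never adds any. For one group of events the premise that no phase can be given is also untrue, because the collection window already fixes the phase. The arms are small, particularly when AE tables are split by cohort, so a single patient can visibly move a reported incidence. These tables carry the trial's safety and tolerability objective.

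**Working it through.** The plan gives no figure on this point, so there is none to reproduce. The check is a trace of the rule followed by simple proportions.

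**1. Trace of the date patterns.** Take first dose on day 1 and last dose on day 84. The on-treatment phase (SAP 6.2.3) then runs to day 84 + 7 = day 91.

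| Start date | End date | Phase under SAP 6.6.2 | What the collection window implies for a non-serious AE |
|---|---|---|---|
| completely missing | day -2 | Baseline | outside the collection window |
| completely missing | day 1 | none | on-treatment |
| completely missing | day 40 | none | on-treatment |
| completely missing | day 100 | none | on- or off-treatment |
| completely missing | missing | none | on- or off-treatment |
| partial, imputed to day 1 | day 40 | On-treatment | on-treatment |

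Rows 2 and 3 are the clear error. A non-serious AE is collected only from first dose, so it is not baseline. It ended by day 91, so it did not start off-treatment. One phase remains, and the SAP does not give it. Rows 4 and 5 are ambiguous between two post-dose phases, and there the SAP has no default.

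**2. Which tables are affected.** In SAP section 12 the n (%) tables for AEs (14.3.2.1 to 14.3.2.12), AEs with outcome of death (14.3.2.13 to 14.3.2.15), SAEs (14.3.4.1 to 14.3.4.3) and AEs leading to discontinuation (14.3.5.1 and 14.3.5.2) belong to one phase or the other. None has an unassigned category. The key subject information tables for SAEs (14.3.4.4) and discontinuation AEs (14.3.5.3) carry no phase restriction. Table 14.3.2.16, on AEs with outcome of death, combines the two phases; whether it would take an event with neither is unclear. All AEs are listed.

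**3. Consistency with the rest of the plan.** SAP 5.2 declares departures from Protocol 8.5.3 for ECG, laboratory shifts and urinalysis, but not for this rule. Elsewhere the SAP resolves missing information cautiously: missing causality counts as drug-related (6.6.2), medications with completely missing dates count as concomitant (8.5), and most day-1 measurements of unknown time count as post-dose (6.2.3 and 6.3).

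**4. Size per affected patient.** The formula is 100 × 1/n, with arm sizes from the 2:1:2 allocation.

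- Pooled, about 138 patients: 138 × 2/5 = 55.2 and 138 × 1/5 = 27.6. So 1/55 = 1.8 points and 1/28 = 3.6 points.
- 12-week cohort, about 100 patients: 40 and 20. So 1/40 = 2.5 points and 1/20 = 5.0 points.
- 4-week cohort, about 38 patients: 38 × 2/5 = 15.2 and 38 × 1/5 = 7.6. So 1/15 = 6.7 points and 1/8 = 12.5 points.

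SAP 8.8.2 counts a patient once per category, so these are maxima. They apply only if the patient has no other counted event in that category. In an arm of 40, one patient can be the difference between 1/40 = 2.5% and 2/40 = 5.0%, on either side of the 3% cut for most common AEs if that cut is applied by arm.

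**The case against.** The strongest reply is that the rule will hardly ever be used. AE start date and time are collected variables (Protocol 6.3.3), patients are asked about health problems since the previous visit (6.3.5), and missing data are queried before clean file (9.4). An onset date known only to the year is not completely missing and goes to the partial-date rules. The rule also takes no account of treatment arm. All of this stands, and it limits the practical weight of the point.

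Four stronger readings are tempting, and the documents do not support them.

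- A reader might infer that any missing start date drops the event. Only completely missing dates do; partial dates are imputed, often to first dose.
- A reader might infer that these events disappear from every AE and SAE summary and survive only in listings. Tables 14.3.4.4 and 14.3.5.3 still cover SAEs and discontinuation AEs. At the first interim analysis an SAE can also be placed by the date it became serious, although the SAP restricts that assignment to one purpose.
- A reader might infer that each lost event lowers a rate by the percentages above. Once-per-category counting means that the effect is often zero.
- A reader might infer that every such event must be post-dose. That argument covers non-serious AEs only. SAEs are recorded from consent, which is sought during the ACS hospitalization, and first dose comes 7 to 28 days after the ACS. An SAE of unknown onset could therefore predate dosing.

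The SAP also does not state that unassigned events are left out of the n (%) tables. That is inferred from the on/off split and the absence of any other category.

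**Conclusion.** The point holds within those limits. SAP 6.6.2 departs, without declaring it, from the protocol's instruction to place every AE in a period. It gives the wrong result for non-serious AEs of wholly unknown onset that ended between first dose and 7 days after last dose. For the other unassigned patterns it lacks a default where one is needed.

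The size is at most one patient per category for each patient affected, on the figures above. Those figures assume that the approximate planned enrolment and cohort split are met at 2:1:2, and that the tables are built as their titles indicate. How many events would be affected cannot be known from the documents. This is a correction worth making because it is cheap and concerns safety counts; it is not a threat to the trial's conclusions.

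**What to change.** Replace both branches that leave the event unassigned with one rule: *the AE will be assigned to the On-treatment phase unless the end date (or, for an SAE, the date it became serious or another recorded SAE date) shows that it began or ended before the first dose of IP*. Flag these events in the AE listing.

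The cost is one SAP sentence and a listing flag. The small downside is that an off-treatment event of unknown onset, or a pre-dose SAE of unknown onset, may be counted as on-treatment. Both errors are in the conservative direction, and the flag lets a reader identify them.

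If the team prefers not to default, the minimum is an unassigned row in the AE tables, with the departure from Protocol 8.5.3 declared in SAP 5.2.

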6.3.3 Variables

The following variables will be collect for each AE;

- AE (verbatim)
- The date and time when the AE started and stopped
- Maximum intensity
- Whether the AE is serious or not

- Investigator causality rating against the IP (yes or no)
- Action taken with regard to IP
- AE caused patient's withdrawal from study (yes or no)
- Outcome.

In addition, the following variables will be collected for SAEs:

- Date AE met criteria for serious AE
- Date Investigator became aware of serious AE
- AE is serious due to
- Date of hospitalization
- Date of discharge
- Probable cause of death
- Date of death
- Autopsy performed
- Causality assessment in relation to Study procedure(s)
- Causality assessment to other medication
- Description of AE.

It is important to distinguish between serious and severe AEs. Severity is a measure of intensity whereas seriousness is defined by the criteria in Section 6.2. An AE of severe intensity need not necessarily be considered serious. For example, nausea that persists for several hours may be considered severe nausea, but not a SAE unless it meets the criteria shown in Section 6.2. On the other hand, a stroke that results in only a limited degree of disability may be considered a mild stroke but would be a SAE when it satisfies the criteria shown in Section 6.2.

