8.5.3 Analysis of safety variables

AEs will be summarised by treatment group by means of counts summaries by Medical Dictionary for Regulatory Activities (MedDRA) System Organ Class and Preferred Term (PT). All AEs will be listed and assigned to on/off treatment period as:

- Baseline period: The time before first administration of IP.
- On treatment: The time from first administration of IP until 7 days after last dose of IP.
- Off treatment: More than 7 days after last dose of IP.

AEs will be assigned to the period where they start.

Laboratory data for haematology and clinical chemistry will be summarized by treatment group. The frequency of changes with respect to normal ranges between baseline and end of treatment will be tabulated. Shifts from normal to abnormal between baseline and end of treatment time point will be evaluated for urinalysis. Descriptive statistics might need to be applied to evaluate some of the reported urine laboratory values changes. The incidence of markedly abnormal values and changes from baseline in the ECG parameters will be summarised by treatment group. Categorical outliers may be presented by numbers but need to be considered in context of inclusion/exclusion criteria. Physical examination and vital signs variables will be summarised by treatment group.

Other safety variables will be summarised as appropriate. Further details will be provided in the SAP.

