8.10.3 Estimate the effect on safety variables

The effect on safety variables will be presented using the Safety Analysis Set by treatment group. Below a detailed description of the summaries that will be used for the purpose:

Adverse Events

AEs will be assigned to the study phases as described in section 6.6.2.

Original:

Copy:

TPCA025 Version 2 (based on TPQA036 Version 2) Effective Date: 27th August 2017 Prior Effective Date: 21st December 2016

Sponsor:	AstraZeneca AB	Protocol/CIP Number:	D7550C00003
CIL Project Number:	40343		

Unless otherwise specified, AEs and SAEs will be summarized using the Safety Analysis Set by treatment group and by cohort of patients. Percentages will be based on the total numbers of subjects in the treatment group.

Subjects with multiple events in the same category will be counted only once in that category. Subjects with events in more than 1 category will be counted once in each of those categories.

Only On-treatment phase up to visit 4 at the first IA and up to the cut-off date at the second IA will be reported for each summary table.

The following summary tables will be reported:

An overview table for all the AEs, only for the On-treatment phase.

The number and percentage of subjects with any AEs for each SOC and PT, only for the On-treatment phase.

The number and percentage of subjects with any SAEs for each for each SOC and PT, only for the On-treatment phase.

The following table will be reported for the first IA only:

The number and percentage of subjects with any non-serious AEs only for the On-treatment phase and only for those categories which show more that 5% of frequency, globally and for each PT.

Additionally, for the second IA, the following summary tables will be reported:

The number and percentage of subjects with AEs with outcome of death for each SOC and PT, only for the On-treatment phase.

The number and percentage of subjects with AEs leading to treatment discontinuation for each SOC and PT in the On-treatment phase.

The following listings will be reported for the second IA:

Listings will also be presented by subject for all AEs using the Safety Analysis Set.

Listing of SAEs will also be presented for enrolled but not randomized subjects and for subjects who were not exposed to treatment.

Laboratory test results for haematology, coagulation and clinical chemistry

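### At the second interim and final analysis, an SAE with a recorded start before first dose that turns serious after it stays in the Baseline phase and enters no SAE count table

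*SAP*

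**What the plan says.** Protocol 8.5.3 gives the general rule: "AEs will be assigned to the period where they start". SAP 6.6.2 repeats it ("AEs will be assigned to the period where they start according to the following algorithm") and covers the pre-dose case directly: "If the AE starts prior to the first dose of IP, then the AE will be assigned to the Baseline phase". It then announces that "The way the SAEs will be assigned to a specific period will be different for the first IA and second IA/final analysis".

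- **First interim.** Three bullets place the SAE by the date it became serious: before first dose is Baseline, first dose through 7 days after last dose is On-treatment, and later is Off-treatment. The following paragraph restricts this: "The SAE assignation is used only to identify cases in which the AE starts as Non-serious in the On-treatment phase", and then turns serious off treatment.
- **Second interim and final analysis.** One special rule is given: "If the AE started in the on-treatment phase and became serious in the off-treatment phase, the AE will be considered as serious from the start". Nothing is said about events that start before first dose.

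On output, SAP 8.8.2 reports On-treatment and Off-treatment separately. SAP Section 12 lists SAE counts in Tables 14.3.4.1 (On), 14.3.4.2 (Off) and 14.3.4.3 (related, On), and fatal AEs in Tables 14.3.2.13 to 14.3.2.15. No Baseline table is listed. SAP 8.10.3 limits the interims further: "Only On-treatment phase up to visit 4 at the first IA", and On-treatment up to the cut-off at the second.

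On collection, Protocol 6.3.1 starts AE recording at first dose but SAE recording at consent. Protocol 6.3.3 collects the start date of every AE and, for SAEs, "Date AE met criteria for serious AE".

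**The concern.** Worsening to a serious event after dosing has begun is something a safety table should show. One AE record can straddle first dose, because it carries both an onset date and a serious-criterion date. If phase follows onset alone, and the pre-dose phase has no table, the event is counted in neither column.

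This also sits oddly with the SAP's cautious choices elsewhere. At the final analysis an on-to-off event counts as serious on treatment. A missing causality assessment counts as drug-related. Under SAP 7.3, an onset with only the day missing, in the month of first dose, is set to the first-dose date if the event continues past it. A fully known pre-dose onset followed by worsening on drug gets the opposite treatment.

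Safety and tolerability is a stated objective (Protocol 2.3) and the arms are small, so a single omitted SAE is visible in a percentage.

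**Working it through.** There is no planned figure to reproduce. The check follows each possible path, from the phase of onset to the phase in which the event became serious, through the rules.

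| Onset → serious | First interim, bullets alone | First interim, with the limiting sentence | Second interim and final | With the fix below (final) |
|---|---|---|---|---|
| Baseline → Baseline | Baseline | Baseline | Baseline | Baseline |
| Baseline → On | On | Baseline | Baseline | On |
| Baseline → Off | Off | Baseline | Baseline | Off |
| On → On | On | On | On | On |
| On → Off | Off | Off for the SAE; non-serious AE in On | On | On |
| Off → Off | Off | Off | Off | Off |

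Baseline is tabulated nowhere. Off is tabulated only at the final analysis.

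1. **Final analysis.** Baseline → On and Baseline → Off both end in Baseline, so neither is in an SAE count table. Baseline → Baseline is also uncounted, as expected for a pre-treatment event. Every SAE that starts on or after first dose is counted.
2. **First interim.** Columns two and three disagree for both Baseline-start paths that turn serious later. The text supports either reading.
3. **Can the case arise?** Protocol Table 1 puts screening at days 1–5 after the ACS and randomization at days 7–28. The interval before dosing runs from 7 − 5 = 2 to 28 − 1 = 27 days. This is the span in which a recorded onset could fall, not a period in which non-serious AEs are routinely collected.
4. **Size per event.** Protocol 8.2 plans about 40 randomized patients per main arm and about 20 on the low dose for 12 weeks. One event is 1/40 = 2.5 percentage points, or 1/20 = 5 points. These are scale figures for a single event. The documents give no expected number of such events, so no total can be calculated.

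**The case against.** The strongest reply is that the data path is mostly closed upstream. The event is by definition non-serious before dosing, and non-serious AEs are not collected then; Protocol Table 1 limits the Visit 1 review to SAEs. Protocol 6.1 lets a deterioration of an existing condition count as an AE, so a site may open a new record with an on-treatment onset. SAP 7.3 moves some partial onset dates to the first-dose date. Start-date phasing is also the protocol's own rule. All of this stands and makes the case narrow. It does not close it: nothing tells sites to open a new record when a pre-dose condition worsens, so the earlier onset date may be entered.

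A reader might infer more than the documents support:

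- **That on-treatment SAEs in general are lost.** They are not. Only those with a recorded onset before first dose are affected.
- **That the first-interim text clearly sends these events to Baseline.** It does not. The bullet above the limiting sentence sends them to On-treatment; the fault is a contradiction.
- **That the events vanish from reporting.** Listing 16.2.7.1 is not restricted by phase, key-subject Table 14.3.4.4 is planned for every subject with an SAE, and deaths have their own Tables 14.3.3.1 and 14.3.3.2.
- **That the safety review committee was shown too few SAEs.** At the first interim an on-to-off event would be an SAE only in Off-treatment tables, which that interim does not produce. But Protocol 8.5.6 gives the committee unblinded AEs, SAEs and safety laboratory data without limiting it to those tables.

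**Conclusion.** The point holds in limited form. At the second interim and final analysis, the SAP's rules leave an event with a pre-dose onset that turns serious after first dose out of the On- and Off-treatment counts of SAEs, related SAEs and fatal AEs. That follows from the text. The first-interim rules contradict each other on the same events.

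How often this happens is unknown and probably low. Each occurrence is worth 2.5 or 5 percentage points in the planned 12-week arms. The conclusion assumes that a site enters the earlier onset date instead of opening a new record. The statement that deaths are still counted assumes the all-deaths tables are phased by date of death, which the SAP does not spell out.

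The correction matters mainly for the final analysis. The SAP is at version 7.0 (May 2020), and its version 4.0 (May 2019) already dealt with updates after the first interim. That interim has probably been run, though the documents do not say so.

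**What to change.** In SAP 6.6.2, for the final analysis, add a rule: an event that starts before first dose and meets a serious criterion on or after first dose is phased by the serious-criterion date. It is On-treatment through 7 days after last dose and Off-treatment after that. Keep the existing on-to-off rule. Reconcile the first-interim bullets with the sentence that limits their use, so that the record shows which one applied. List the change in SAP 5.2, because it departs from the start-date rule in Protocol 8.5.3.

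The cost is a few lines of SAP text and one derivation. The serious-criterion date is already collected, and SAP 7.3 already has an imputation rule for it. The downside is small: a few events with pre-dose onset will count as on- or off-treatment SAEs.
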